#### 10.1.9.2 STUDY RECORDS RETENTION

Study documents should be retained for a minimum of 2 years after the last approval of a marketing application in an ICH region and until there are no pending or contemplated marketing applications in an ICH region or until at least 2 years have elapsed since the formal discontinuation of clinical development of the study intervention. These documents should be retained for a longer period, however, if required by local regulations. No records will be destroyed without the written consent of the Sponsor, if applicable. It is the responsibility of the Sponsor to inform the investigator when these documents no longer need to be retained.

---

#### 10.1.10 PROTOCOL DEVIATIONS

A protocol deviation is any noncompliance with the clinical trial protocol, ICH GCP, or Project Management Plan requirements. The noncompliance may be either on the part of the patient, the investigator, or the study site staff. As a result of deviations, corrective actions are to be developed by the site and implemented promptly.

These practices are consistent with ICH GCP:

- 4.5 Compliance with Protocol, sections 4.5.1, 4.5.2, and 4.5.3
- 5.1 Quality Assurance and Quality Control, section 5.1.1
- 5.20 Noncompliance, sections 5.20.1, and 5.20.2

It is the responsibility of the site investigator to use continuous vigilance to identify and report deviations within 10 working days of identification of the protocol deviation, or within 10 working days of the scheduled protocol-required activity. All deviations must be addressed in study medical records, reported to Leo Lens Technology or its designee. Protocol deviations must be sent to the reviewing IRB per their policies. The site investigator is responsible for knowing and adhering to the reviewing IRB requirements. Further details about the handling of protocol deviations will be included in the Project Management Plan.

---

#### 10.1.11 PUBLICATION AND DATA SHARING POLICY

Leo Lens Technology, as the Sponsor, has proprietary interest in this study. Authorship and manuscript composition will reflect joint cooperation between the Principal Investigator and Leo Lens Technology personnel. Authorship will be established prior to the writing of the manuscript. No individual publications will be allowed prior to completion of the final report of the study, except as agreed with Leo Lens Technology.

This study will be registered on the ClinicalTrials.gov registry.

---

#### 10.1.12 CONFLICT OF INTEREST POLICY

Due to potential conflict of interest, patients or members of the patient's household who are employees of the investigative site are not eligible for enrollment in the study.

### 10.2 ADDITIONAL CONSIDERATIONS

Investigational site staff will be instructed to follow their institutional infection control standard procedures and to consider additional measures during periods of community transmission of conditions, such as COVID-19. These additional measures may include:

- Contacting patients the day before a scheduled appointment for a number of reasons, including:
  - To determine if they are experiencing any signs or symptoms of possible infections. Such COVID-19-related symptoms include fever, cough, shortness of breath, and sore throat
  - To determine if the patient has tested positive for COVID-19, been in contact with someone who is known or suspected to be positive for COVID-19, or traveled to an area of in which there is or has been an outbreak of COVID-19 cases
  - To reschedule patients who are experiencing respiratory symptoms and instructing them to seek appropriate medical attention. This requires removal of the LL-BMT1 contact lenses if they are in the on-treatment portion of the study. Removal under these circumstances can be done by the subject or by site personnel.
  - To remind patients to contact the investigational site if they develop respiratory or other COVID-related symptoms on the morning before a scheduled examination or if they have had changes to their health status since their last visit

Upon arrival at the investigational site, patients should be assessed for fever and provided with proper protective equipment (PPE; eg, face masks), if they are not already using PPE.

Equipment that is meant to be used on more than one person should be draped to prevent possible contamination and appropriately cleaned before and after each use. Additional measures should also be considered, including:

- Posting guidelines for the reduction of risk of coronavirus transmission
- Reminding patients of the need for social distancing/ consider having patients wait outside of the investigational site (eg, in their vehicles until they are ready to be seen)
- Restricting non-essential individuals accompanying patients from patient areas
- Providing supplies for respiratory hygiene and cough etiquette, including 60% to 95% alcohol-based hand sanitizer, no-touch receptacles for waste disposal, face masks, and tissues at healthcare facility entrances, waiting rooms, patient check-ins, etc.
- Reminding patients to wash hands and/or use hand sanitizer frequently

Study visits and assessments should be rescheduled at the discretion of the Investigator when there is a perceived increased risk of coronavirus transmission to patients and/or investigational site staff.

### 10.3 ABBREVIATIONS

AE	adverse event
BCVA	best-corrected visual acuity
CFR	Code of Federal Regulations

CLDEQ-8	Contact Lens Dry Eye Questionnaire-8
CONSORT	Consolidated Standards of Reporting Trials
eCRF	electronic Case Report Forms
ETDRS	Early Treatment Diabetic Retinopathy Study
FDA	Food and Drug Administration
GCP	Good Clinical Practice
HIPAA	Health Insurance Portability and Accountability Act
ICH	International Conference on Harmonisation
IFU	instructions for use
IND	Investigational New Drug
IOP	intraocular pressure
IRB	Institutional Review Board
ITT	intent-to-treat
IUD	intrauterine device
IWRS	interactive web response system
LASIK	laser-assisted in situ keratomileusis
MedDRA	Medical Dictionary for Regulatory Activities
NDA	New Drug Application
OAG	open-angle glaucoma
OHRP	Office for Human Research Protections
OHT	ocular hypertension
PI	prescribing information
POAG	primary open-angle glaucoma
PP	per-protocol
PPE	proper protective equipment
PRK	photorefractive keratectomy
ROCK	Rho kinase
QC	quality control
RK	radial keratotomy
SAE	serious adverse event
SAP	statistical analysis plan
SMILE	small incision lenticule extraction
US	United States

#### 10.4 PROTOCOL AMENDMENT HISTORY

Version	Date	Description of Change	Brief Rationale
1.1	11/19/20	Based upon input from the U.S. Food and Drug Administration, the numbers of subjects to be entered and dosed in the study was changed FROM “5-7” TO “5”. This impacts several sections of the protocol including the Synopsis, Schema, Overall Design, and Sample Size Determination section. Further, clarifications were added to the Schema and Safety and Other Assessment sections to assist the Investigator.	Amendment based on input from U.S. Food and Drug Administration.

1.2	12/21/20	Based upon input from the IRB, the protocol was amended to include best corrected visual acuity and slit lamp exam to all visits prior to the baseline visit.	Amendment based on input from IRB.

12 ATTACHMENTS

Patient/Subject #: \_\_\_\_\_  
Date: \_\_\_/\_\_\_/\_\_\_ Time: \_\_\_\_\_

**CONTACT LENS QUESTIONNAIRE-8  
(CLDEQ-8)**

1. Questions about **EYE DISCOMFORT**:

a. During a typical day in the past 2 weeks, **how often** did your eyes feel discomfort while wearing your contact lenses?

- 0 Never
- 1 Rarely
- 2 Sometimes
- 3 Frequently
- 4 Constantly

When your eyes felt discomfort with your contact lenses, **how intense** was this feeling of discomfort...

b. At the end of your wearing time?

Never have it	Not at All Intense				Very Intense
0	1	2	3	4	5

2. Questions about **EYE DRYNESS**:

a. During a typical day in the past 2 weeks, **how often** did your eyes feel dry?

- 0 Never
- 1 Rarely
- 2 Sometimes
- 3 Frequently
- 4 Constantly

When your eyes felt dry, **how intense** was this feeling of dryness...

b. At the end of your wearing time?

Never have it	Not at All Intense				Very Intense
0	1	2	3	4	5

3. Questions about **CHANGEABLE, BLURRY VISION**:

a. During a typical day in the past 2 weeks, **how often** did your vision change between clear and blurry or foggy while wearing your contact lenses?

- 0 Never
- 1 Rarely
- 2 Sometimes
- 3 Frequently
- 4 Constantly

When your vision was blurry, **how noticeable** was the changeable, blurry, or foggy vision ...

b. At the end of your wearing time?

Never have it	Not at All Intense				Very Intense
0	1	2	3	4	5

4. Question about **CLOSING YOUR EYES**:  
During a typical day in the past 2 weeks, **how often** did your eyes bother you so much that you wanted to close them?

- 0 Never
- 1 Rarely
- 2 Sometimes
- 3 Frequently
- 4 Constantly

5. Question about **REMOVING YOUR LENSES**:  
How often during the past 2 weeks, did your eyes *bother you so much* while wearing your contact lenses that you felt as if you needed to stop whatever you were doing and take out your contact lenses?

- 1 Never
- 2 Less than once a week
- 3 Weekly
- 4 Several times a week
- 5 Daily
- 6 Several times a day

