Description of Site Enrolling Patients:	Up to 2 sites within the United States (US)
Description of Study Intervention:	LL-BMT1 is a US Food and Drug Administration (FDA)-classified Group 4 extended-wear contact lens that has bimatoprost printed onto the anterior surface of the contact lens in one set concentration. The coating of the anterior surface does not obstruct the optic zone, and the bimatoprost elutes from both the concave and convex surfaces of the lens. LL-BMT1 is designed to lower the IOP of patients with POAG or OHT and be worn for 1 week (7 days, 6 nights). Patients will wear LL-BMT1 lenses for 1 week.
Study Duration:	3 to 4 months
Patient Treatment Duration:	1 week for each patient

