**Day -6 (Visit 4): Acclimation (second nonmedicated lens insertion)**

- Concomitant medications
- AEs
- BCVA
- Biomicroscopy
- Nonmedicated lens insertion (new lens)

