Five (5) patients will receive LL-BMT1 contact lenses [REDACTED] inserted into each eye at the Day 1 visit, where they will remain until the Day 7 Visit, at which time the lenses will be removed. Patients will not remove the lenses themselves during the study. During the 7-day treatment period, patients will be assessed for safety and IOP reduction which requires removal and reinsertion of LL-BMT1 on Day 1 and Day 4. AEs will be monitored, as will other safety measures, including BCVA, slit-lamp biomicroscopy, and contact lens protein deposit. Patients will attend a follow-up visit on Day 8, during which heart rate/blood pressure, BCVA, and IOP will be assessed. If a patient's IOP is decreased from baseline by  $\geq 3$  mmHg at the Day 8 Visit, a Day 9 Visit will be performed in order to reassess IOP.

The primary focus of this safety study will be a comprehensive descriptive assessment of safety endpoints. No formal study hypothesis will be tested.

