## 5 STUDY POPULATION

### 5.1 INCLUSION CRITERIA

In order to be eligible to participate in this study, an individual must meet all of the following criteria:

1. Male or female, at least 18 years of age at the Screening Visit
2. Diagnosed with POAG or OHT in both eyes
3. At least one eye (called the study eye) must have an untreated IOP between 22 mmHg and 34 mmHg (inclusive) as measured at 9 am during the Baseline Visit. For eyes receiving IOP treatment, untreated IOP will be assessed following a required washout period as outlined below:
  - 4 days washout for parasympathomimetic and topical or systemic carbonic anhydrase inhibitors
  - 2 weeks washout for sympathomimetics and alpha agonists
  - 4 weeks washout for beta adrenergic blocking agents, combination product, Rho kinase (ROCK) inhibitors, and prostaglandin agonists
4. If the fellow eye does not meet inclusion criterion #3 above, it must have an untreated IOP (following washout, if applicable) within 5 mmHg of the study eye without exceeding the 34 mmHg maximum (eg, a study eye IOP of 22 mmHg and a fellow eye IOP of 17 mmHg are allowed).
5. BCVA of Early Treatment Diabetic Retinopathy Study (ETDRS) of 50 letters or better (Snellen equivalent of 20/100 or better) in each eye
6. Women of child-bearing potential must not be pregnant or lactating, must have a negative pregnancy test at screening and must be practicing an adequate method of birth control, including intrauterine device (IUD); oral, dermal (“patch”), implant or injected contraceptives; tubal ligation; or barrier methods with spermicide
7. No adverse reactions to nonmedicated contact lenses during the 2-week acclimation screening
8. Score of 0-11 on CLDEQ-8, administered at the end of the 2-week acclimation screening
9. Willing and able to comply with the study procedure and sign a written informed consent

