### 9.4.2 SAFETY ANALYSES

Analysis of treatment-emergent AEs will be conducted based on the safety population. Safety endpoints include:

- AEs
- Concomitant medications
- Heart rate and blood pressure
- BCVA
- IOP
- Biomicroscopy
- Conjunctival hyperemia

Ocular events will be reported on an eye level, while non-ocular events will be on a patient level.

AEs will be coded using the Medical Dictionary for Regulatory Activities (MedDRA). For each AE reported, the number and percent of patients/eyes will be tabulated based on the preferred term and ocular and non-ocular AEs will be reported separately. The tables will be generated by relationship to treatment as well as by system organ class and severity.

The primary safety endpoint is the AE rate ( $100 \times [\text{number of AEs} / \text{number of eyes exposed to treatment}]$ ). The modified safety set will be used for a sensitivity analysis of the primary safety endpoint.

*Secondary safety endpoints:*

- Percent of patients with  $\geq 5$ -mmHg increase from baseline in IOP at each visit
- Abnormal slit-lamp biomicroscopy findings at the Baseline, Day 1, and Day 7 Visits
- Contact lens protein deposits at the Day 7 Visit
- Change from baseline in CLDEQ-8 results at the Day 7 Visit

Pre-existing AEs, those identified after enrollment but before treatment with LL-BMT1, will be tabulated for all consented patients.

---

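### The Day 7 CLDEQ-8 looks back 2 weeks, so about half of its recall window predates LL-BMT1 and the change from Baseline can be diluted toward zero

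*Protocol*

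**What the plan says.** The form is in Protocol Section 12. Items 1a, 2a, 3a and 4 open with "During a typical day in the past 2 weeks", and item 5 with "How often during the past 2 weeks". The intensity items 1b, 2b and 3b carry no recall period of their own; they follow on from the frequency items and ask about the feeling "At the end of your wearing time".

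The Schedule of Activities (Protocol Section 1.3) places the form at Baseline, at Day 7 and at the Early Termination Visit. At Baseline it also decides eligibility: inclusion criterion 8 requires a "Score of 0-11 on CLDEQ-8, administered at the end of the 2-week acclimation screening". The endpoint in Protocol Section 9.4.2 is "Change from baseline in CLDEQ-8 results at the Day 7 Visit", and SAP Sections 5.2 and 6.8 repeat it.

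On lens wear, the Schema (Protocol Section 1.2) has the first nonmedicated lens removed on Day -7, and the second inserted on Day -6 and removed on Day 0. Protocol Section 4.1 has LL-BMT1 "inserted into each eye at the Day 1 visit, where they will remain until the Day 7 Visit". Neither document changes the recall period at Day 7, tells patients which lens to answer for, or says how to read a score that covers two lenses.

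**The concern.** The change score is meant to show how LL-BMT1 compares with the nonmedicated lens in the same patient. A form that looks back 14 days after 7 days of LL-BMT1 asks the patient to describe both lenses at once.

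The direction matters. Patients reach treatment only if they had no adverse reaction to the nonmedicated lenses and scored 0-11 at Baseline (Protocol Section 5.1, criteria 7 and 8). The week shared by the two windows is therefore selected to be well tolerated, and including it in the Day 7 answer can hide poorer tolerability of LL-BMT1. The study expects to reveal no safety concerns (Protocol Section 9.1), so a change pulled toward zero supports the expected conclusion. With 5 patients or with many, averaging does not remove a systematic pull.

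**Working it through.** **Inputs.** Recall of 14 days (Section 12). LL-BMT1 in place Day 1 to Day 7 (Section 4.1). Second nonmedicated lens Day -6 to Day 0, first one out on Day -7 (Section 1.2). CLDEQ-8 at Day 0 and Day 7 (Section 1.3).

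**The plan's own figure.** Day 1 to Day 7 inclusive is 7 - 1 + 1 = 7 days and 7 - 1 = 6 nights. This matches the wear period in the Synopsis.

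**Calendar days.** The 14 days ending on Day 7 are Day -6 to Day 7. LL-BMT1 covers Days 1 to 7, so 7/14 = 50%. The other 7 days (Day -6 to Day 0) come before it.

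**Elapsed time.** The documents fix few clock times, so these are assumptions. In the base case, insertions and earlier removals are at 9 am, and the Day 7 removal and form are at 4 pm. The window then starts at 4 pm on Day -7.
- LL-BMT1: 6 days + 7 h = 6.29 days; 6.29/14 = 44.9%.
- Nonmedicated lens: 9 am Day -6 to 9 am Day 0 = 6.00 days; 6.00/14 = 42.9%.
- Lens-free: 14 - 6.29 - 6.00 = 1.71 days; 1.71/14 = 12.2%.

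Moving the clock times within the working day gives LL-BMT1 44-46%, nonmedicated 40-44% and lens-free 12-14%. Of lens-wearing time alone, LL-BMT1 is 50-53%.

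**Overlap.** The Baseline window runs from Day -14 to Day 0, and the Day 7 window from Day -7 to Day 7. They share 0 - (-7) = 7 of 14 days.

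**Effect on the change score.** Let N be the score a patient would give for the nonmedicated lens alone, T the score for LL-BMT1 alone, and w the weight the patient gives to LL-BMT1 time. Count time before insertion as N.
- Baseline = N; Day 7 = wT + (1 - w)N; change = w(T - N).
- Equal weighting of days (assumption): w is about 0.44 to 0.53 across the ways of counting above. A true worsening of 4 points (an illustration) would show as 4 × 0.44 = 1.8 to 4 × 0.53 = 2.1.
- Intensity items answered wholly for LL-BMT1 (assumption): the maximum score is 4+5+4+5+4+5+4+6 = 37, of which 1b, 2b and 3b hold 15 and the five 2-week items hold 22. If the true difference is spread in proportion to these maxima and w = 0.50 elsewhere, the share seen is (22 × 0.50 + 15)/37 = 26/37 = 0.70, and 4 points show as 2.8.
- Only recent days recalled: w approaches 1 and dilution disappears.

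**One item answered literally.** A patient who wanted LL-BMT1 out once every day, and never the nonmedicated lens, has about 7 such days in 14. On item 5 that is the several-times-a-week option (4) rather than the daily one (5). Against a Baseline answer of never (1), the change is 3 instead of 4.

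**Early termination.** A form completed on Day 4 would hold 4 LL-BMT1 calendar days of 14, or 29%.

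**The case against.** Three stronger readings are tempting, and the documents do not support them.

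- A reader might infer that the change score is itself half nonmedicated experience. It is not. About half of the recall window behind the Day 7 score precedes LL-BMT1; the change subtracts a Baseline score that reflects no LL-BMT1 wear, and the consequence is dilution.
- A reader might infer that a halved change is established. Halving needs every day to count equally in every item. Items 1b, 2b and 3b, with 15 of 37 points, have no 2-week wording, and at Day 7 the lens just taken out is LL-BMT1. The frequency items ask about a typical day, not an average, and item 5 is ordinal. Halving is near the upper end of the plausible range.
- A reader might infer that this is the only patient-reported information on tolerability. Protocol Section 8.3.4 has the investigator open each post-Baseline visit with a general question on how the patient has felt, then directed questions. Discomfort with LL-BMT1 can be recorded there with an onset date, and the adverse event rate is the primary endpoint. CLDEQ-8 is the only questionnaire endpoint.

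It is also fair to say that nothing turns on this endpoint alone: no hypothesis is tested, no threshold is set for CLDEQ-8 change, and line listings are planned for each patient. All of this limits the size and weight of the problem. It does not remove the overlap or change its direction, and no passage in either document deals with it.

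**Conclusion.** The point holds as a minor measurement weakness. About half of the Day 7 recall window is nonmedicated or lens-free time (7 of 14 calendar days; about 54-56% by elapsed time under the assumed clock times), and it shares about 7 of 14 days with the Baseline window. The change from Baseline can be diluted toward zero. The upper end, about half, assumes equal weighting of days. If the intensity items are answered for LL-BMT1, about 70% of a true difference would show, and if only recent days are recalled, nearly all of it. The documents cannot settle which applies.

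As the plan stands, a CLDEQ-8 change near zero is weak evidence that LL-BMT1 is as well tolerated as the nonmedicated lens. It is minor because the endpoint is secondary and descriptive in 5 patients, and no error rate or sample size depends on it.

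**What to change.** On the Day 7 and Early Termination forms, instruct patients to answer every item only for the period since the LL-BMT1 lenses were first inserted on Day 1. Anchor the wording to Day 1 and not to the current lenses: LL-BMT1 is taken out and put back on Days 1 and 4, and the Day 7 removal is listed before the questionnaire, so a reference to current lenses could be read in several ways.

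Keep the printed 2-week form at Baseline. There it covers nonmedicated wear and the short gap between the two lenses, and it serves inclusion criterion 8, so eligibility is untouched and no second Baseline form is needed.

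In SAP Section 6.8, state that the recall lengths differ (2 weeks at Baseline, about 1 week at Day 7), and that item 5's option for less than weekly occurrence has little meaning over one week. If Day 7 forms have already been completed as printed, state the overlap as a limitation and do not read a null change as evidence of tolerability.

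The cost is one instruction on two forms and a short SAP paragraph. The downside is a non-standard recall period at Day 7, which makes the scores less comparable with the instrument's usual use.

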1 INTRODUCTION

This statistical analysis plan (SAP) provides a comprehensive and detailed description of analyses and reporting of data for LL-BMT1 study protocol LL-BMT10001. The purpose of the SAP is to ensure the credibility of the study findings by pre-specifying the statistical approaches to the analysis of study data prior to data base lock.

1.1 Changes from Protocol

Not applicable.

2 STUDY OBJECTIVES

2.1 Primary Objective

The primary objective of this study is to evaluate the safety of LL-BMT1 in patients with POAG or OHT.

2.2 Secondary Objective

The secondary objectives of this study are:

- To evaluate the safety and tolerability of LL-BMT1 in patients with POAG or OHT, and
- To evaluate efficacy by IOP-lowering effects of LL-BMT1 in patients with POAG or OHT.

3 STUDY DESIGN

This study is an open-label, phase 2a clinical study consisting of 5 patients at up to 2 sites within the United States, each with a treatment duration of 1 week. All patients will be assigned to the study intervention (LL-BMT1 lenses) and will wear then for 1 week.

3.1 Sample Size Considerations

Due to the exploratory nature of this study, no formal power sample size calculation has been performed. An empirical sample size of at least 5 evaluable patients is planned. Assuming a 10-20% drop-out non-evaluable rate, up to 7 patients (7 study eyes) will be consented to begin acclimation screening. Those who are consented but fail acclimation screening will be replaced until at least 5 patients successfully complete the acclimation screening. Five patients who pass acclimation screening will be enrolled as patients for study treatment.

